4.5. Dosing Delays/Dose Modifications

4.5.1. Patients experiencing unacceptable toxicity directly attributable to the study drugs should temporarily stop treatment according to the guidelines in the dose adjustment schema.

4.5.2. Toxicity grading will be according to the NCI CTCAE, v4. To prevent unnecessary morbidity, the following guidelines for dose adjustment for drug-related toxicities are recommended.

4.5.3. **TKI:** dose modifications will be done according to institutional guidelines. The following guidelines may be used for dose adjustments:

4.5.3.1. Non-Hematologic Toxicity

- **Grade 2:** Patients with persistent grade 2 toxicity that is considered clinically significant, unresponsive to appropriate therapy, may have treatment held until the toxicity has resolved to grade ≤ 1 . TKI may then be resumed at the same dose the patient was receiving at the time treatment was interrupted. If the grade 2 toxicity recurs, TKI may be held until the toxicity has resolved to grade 1. Treatment may then be resumed with a one dose level reduction.
- **Grade 3-4:** If a patient experiences Grade 3-4 toxicity that is considered clinically significant and related to TKI, therapy may be withheld until the toxicity has resolved to Grade ≤ 1 . TKI may then be resumed with a one dose level reduction.

4.5.3.2. Hematologic Toxicity

If granulocytes are $<0.5 \times 10^9/L$ or platelets are $<40 \times 10^9/L$, hold therapy until granulocytes are above $10^9/L$ and platelets are above $60 \times 10^9/L$, then resume therapy.

If recovery takes more than 2 weeks, resume TKI at 1 dose level reduction from the dose the patient was receiving at the time therapy was interrupted.

If recovery takes less than 2 weeks, resume TKI at the same dose the patient was receiving at the time treatment was interrupted. If myelosuppression recurs, resume TKI at one dose level reduction from the dose the patient was receiving at the time the treatment was interrupted.

If a similar degree of toxicity returns, a further dose reduction by one dose level can be performed, using the above procedures.

4.5.3.3. The usual dose levels for dose adjustments are as follows:

Imatinib (mg/d)	Dasatinib (mg/d)	Nilotinib (mg/d)
800	140	800
600	100	600
400	70	400
300	50	300
200	40	200
100	20	150

4.5.3.3.1. The maximum allowable daily doses of TKI are: dasatinib 140 mg/d, nilotinib 800 mg (usually as 400 mg BID), and imatinib 800 mg.

4.5.3.4. Modifications of dose schedules other than the above will be allowed within the following guidelines:

- Further dose reductions can be made to keep toxicity grade ≤ 2 .
- Dose adjustments by more than 1 dose level at a time can be considered when judged in the best interest of the patient (e.g., neutropenia with sepsis, bleeding requiring platelet transfusions) when toxicity has resolved.
- A patient who has had a dose reduction because of any reason may have their dose re-escalated provided the patient has remained free of toxicity requiring dose adjustments as defined above for at least 1 month. Escalation will be made by 1 dose-level increments only, and not more frequent than every month.

4.5.4. **AZA:** dose modifications for toxicity will be done according to the following guidelines:

4.5.4.1. Non-Hematologic Toxicity

4.5.4.1.1. **Persistent Grade 2:** Patients with persistent grade 2 toxicity that is considered clinically significant, unresponsive to appropriate therapy, may have treatment held until the toxicity has resolved to grade ≤ 1 . Therapy may then be resumed at the same dose the patient was receiving at the time treatment was interrupted. If the grade 2 toxicity recurs, therapy may be held until the toxicity has resolved to grade 1. Treatment may then be resumed with a one dose level reduction.

4.5.4.2. **Grade 3-4:** If a patient experiences Grade 3-4 toxicity that is considered clinically significant and possibly related to AZA, therapy must be withheld until the toxicity has resolved to Grade ≤ 1 . Treatment may then be resumed with a one dose level reduction. If toxicity recurs, additional dose reductions may be implemented according following the same general guidelines.

4.5.4.3. If unexplained reductions in serum bicarbonate $< 20\text{mEq/L}$ occur, the dosage should be reduced by 50% on the next course. Similarly, if unexplained elevations of BUN or serum creatinine occur, the next cycle should be delayed until values return to normal or baseline and the dose should be reduced by 50% on the next treatment course.

4.5.4.4. Hematologic Toxicity

- 4.5.4.4.1. If neutrophils are $<0.5 \times 10^9/L$ and/or platelets are $<40 \times 10^9/L$, hold therapy until granulocytes are above $1 \times 10^9/L$ and platelets are above $60 \times 10^9/L$, then resume therapy.
 - 4.5.4.4.2. If recovery takes more than 2 weeks, resume therapy at 1 dose level reduction from the dose the patient was receiving at the time therapy was interrupted.
 - 4.5.4.4.3. If recovery takes less than 2 weeks, resume therapy at the same dose the patient was receiving at the time treatment was interrupted. If myelosuppression recurs, resume therapy at one dose level reduction from the dose the patient was receiving at the time the treatment was interrupted.
 - 4.5.4.4.4. If a similar degree of toxicity returns, a further dose reduction by one dose level can be performed, using the above procedures.
 - 4.5.4.4.5. Patients in whom the toxicity occurs or persists beyond the planned completion of drug administration for the cycle will have the dose reductions implemented in subsequent cycles provided the toxicity has resolved as specified above.
 - 4.5.4.4.6. There will be no making up for missed doses.
- 4.5.4.5. Modifications of dose schedules other than the above will be allowed within the following guidelines:
- 4.5.4.5.1. Further dose reductions can be made to keep clinically significant, AZA-related toxicity grade ≤ 2 . However, the lowest acceptable dose level is -4.
 - 4.5.4.5.2. Dose adjustments by more than 1 dose level at a time can be considered when judged in the best interest of the patient (e.g., neutropenia with sepsis, bleeding requiring platelet transfusions) when toxicity has resolved. The reason for this reduction will be discussed with the PI and the drug supplier and documented in the medical record.
 - 4.5.4.5.3. A patient who has had a dose reduction because of any of the reasons mentioned above may have their dose re-escalated provided the patient has remained free of toxicity

requiring dose adjustments as defined above for at least 1 month. Escalation will be made by 1 dose-level increments only, and not more frequent than every month.

4.5.5. **Dose Escalation:** Patients that do not achieve an improvement in molecular response after 3 months (eg., from major to complete or from non-major to major) and have experienced no grade ≥ 3 toxicity may have the dose of AZA escalated by one dose level. Patients who have had a prior dose reduction of AZA and who have no toxicity for at least 1 month of therapy may increase the dose of AZA following the guidelines mentioned above. Dose escalation of the TKI is also allowed according to institutional guidelines. However, concomitant dose escalation of the two agents is not allowed. Patients who have had dose escalation of TKI cannot have dose escalation of AZA within 2 months of this escalation.

4.5.6. Occasional missed doses of TKI will not be considered a deviation. Missed doses of ≥ 2 weeks without adequate justification will be considered a protocol deviation.

4.5.7. **Duration of Therapy:** Patients may receive therapy for six cycles. After completion of the 6th cycle, patients may continue therapy if in the opinion of the investigator there is clinical benefit provided there has been no grade 3 or higher non-hematologic toxicity attributable to AZA at the doses being administered.

4.5.7.1. Patients who achieve a major or complete molecular remission can hold therapy with AZA and/or TKI and be monitored with PCR. If there is reappearance of transcripts detectable by PCR, therapy with one or both agents can be resumed at the doses being administered at the time treatment was interrupted.

4.5.8. **Concomitant Medications**

4.5.8.1. Patients may not receive any other treatment for CML while on study. This includes the use of hydroxyurea and anagrelide.

4.5.8.2. The use of other medications for management of comorbidities or adverse events is allowed as clinically indicated.

5. **Evaluation During Study**

5.1. **Pretreatment Evaluation** (within 7 days from treatment start, unless otherwise specified)

5.1.1. A complete history and physical examination including performance status.

5.1.2. CBC, platelet count and differential (differential not required if $WBC < 0.5 \times 10^9/L$), total bilirubin, SGPT (or SGOT), and creatinine within 1 week.

- 5.1.3. Bone marrow aspirate for morphology and cytogenetics or FISH (if not done within 3 months).
- 5.1.4. Pregnancy test (blood or urine) for female patients of childbearing potential within 7 days before initiation of study drug dosing.
- 5.1.5. Peripheral blood and/or bone marrow for quantitative PCR (QPCR) (if not done within 3 months).
- 5.1.6. Peripheral blood and/or bone marrow for correlative studies (optional – Appendix A, B & C). Not all optional samples may be collected.

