3.2. Exclusion Criteria

- 3.2.1. Patients receiving any other investigational agents
- 3.2.2. Patients who are pregnant or breast-feeding
- 3.2.3. Patients with clinically significant heart disease (NYHA Class III or IV)
- 3.2.4. Known or suspected hypersensitivity to azacitidine or mannitol.
- 3.2.5. Patients with advanced malignant hepatic tumors.

4. Treatment Plan

4.1. **TKI:** Patients will continue receiving TKI at the dose they had been receiving during the last 6 months.

4.2. **AZA:**

Phase I: patients will be treated in cohorts of 3. The starting dose will be dose level 0 (50 mg/m²/d x 3 days subcutaneous or intravenous; Table 1).

4.2.1. At least 3 patients will be entered at each level. All patients treated at any one dose level must have been observed for at least four weeks before escalating to the next dose level. Patients who come off study prior to the first four weeks and have not experienced a DLT will be replaced.

Table 1: Dose escalation levels	
Dose level	AZA (mg/m ² /d x 3 days)
-3	25 (1 day only)
-2	25 (2 days only)
-1	25
0	50
1 (Target dose)	75
2	75 (for 5 days)
3	75 (for 7 days)

4.2.2. Dose escalation will be done as follows:

Dose-limiting toxicity in	Result
0/3	Escalate to next level
1/3	Enter 3 more patients
≥2/3 or ≥ 2/6	MTD exceeded. This dose level will be declared the maximally administered dose. Expand previous level to include a total of 6 patients if not already accrued to this number.

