4.2.3. Definition of Dose-Limiting Toxicity (DLT)

4.2.3.1. DLT will be defined by events that are clinically significant and possibly related to study drug occurring during the first 4 weeks (1 cycle) of therapy.

4.2.3.2. Non-hematologic DLT is defined as grade 3 or 4 toxicity (NCI common criteria, version 4.0) that is clinically significant and

considered to be at least possibly related to the study drug. Grade 3 or 4 nausea, vomiting and diarrhea will be considered DLT only if not controlled by optimal therapy.

4.2.3.3. Grade 3 biochemical abnormalities (e.g., lipase or bilirubin elevation) will only be considered DLT if accompanied by clinical consequences. Grade 3 or 4 electrolyte abnormalities will only be considered DLT if possibly related to study drug and not corrected by optimal replacement therapy.

4.2.3.4. Hematologic DLT is defined as grade ≥ 3 neutropenia and/or thrombocytopenia with a hypocellular bone marrow lasting for 6 weeks or more after the start of a course. (In case of a normocellular bone marrow, 8 weeks with pancytopenia will be considered DLT). Anemia will not be considered for the definition of DLT.

4.2.4. If dose-level 0 exceeds MTD, subsequent patients will be treated at dose level -1. Additional cohorts at lower doses (down to dose level -4) may be included if higher doses exceed MTD. If dose level -4 exceeds MTD, the study will be terminated.

4.3. **Phase II:** The dose to be used for the phase II portion of the study is $75\text{mg}/\text{m}^2$ daily for 3 days, unless MTD is defined at a lower dose level in the phase I portion of the study in which case that would become the dose to be used for the phase II portion. Other dose levels shown in Table 1 will be used for dose adjustments for toxicity or lack of improvement (as described in section 4.5.5) during therapy. For phase II portion of the study, if at any time patients need to be escalated to dose level +2 or +3, if at any time 33% or more of patients experience DLT at this dose level during the first cycle they receive at this dose, this would be considered to have exceeded MTD and that dose level should not be used any further.

4.4. Treatment with AZA (in both phase I and phase II) may be repeated every 28 days. The start of subsequent cycles may be delayed to allow for recovery of any adverse events to grade 1 or less.

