9.2.1.1. Three patients will be enrolled at the starting dose level

9.2.1.2. If 0/3 patient experiences DLT at a given level, enroll three patients to the next higher dose level

9.2.1.3. If 1/3 patient experiences DLT at a given level, enroll additional three patients to the same dose level

9.2.1.4. If 2/3 or 2/6 patients experience DLT at a given level, the MTD has been exceeded and dose escalation will be stopped. Up to three additional patients will be enrolled at the next lower dose level if only 3 patients were treated at that level.

9.2.2. MTD is defined as the highest dose level in which 6 patients have been treated and one or fewer patient experiences DLT.

The MTD identified in phase I part will be recommended for phase II. If MTD is not determined, the highest AZA level of 75 mg/m²/d x 3 days will be used as the recommended phase II dose.

A maximum of 18 patients will be accrued for phase I part. The data from the 6 patients treated at the recommended phase II dose level (MTD or 75 mg/m²/d x 3 days if MTD is not determined) will be used in phase II part.

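### Individual AZA escalation under section 4.5.5 has no MTD ceiling, and the 33% DLT stop in 4.3 covers only phase II patients at levels +2 and +3

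*Combined protocol and SAP*

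**What the plan says.** All references are to the combined protocol and SAP.

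- **Section 4.5.5.** A patient without molecular improvement after 3 months and without grade 3 or higher toxicity "may have the dose of AZA escalated by one dose level". The section's other limits concern the TKI: the two agents may not be escalated together, and AZA may not go up within 2 months of a TKI escalation. It names no phase and sets no condition on the higher level.
- **Section 4.3.** The phase II dose is 75 mg/m² for 3 days (level 1), or a lower level if the MTD is set there. It continues: "Other dose levels shown in Table 1 will be used for dose adjustments for toxicity or lack of improvement", with a reference to 4.5.5. For the phase II portion, "if at any time patients need to be escalated to dose level +2 or +3", a level at which 33% or more have a DLT in their first cycle there is closed: "this would be considered to have exceeded MTD and that dose level should not be used any further".
- **Section 4.2.1 (phase I).** "All patients treated at any one dose level must have been observed for at least four weeks before escalating to the next dose level". Section 4.2.2 and 9.2.1.4 stop cohort escalation at 2 of 3 or 2 of 6 DLTs.
- **Section 9.2.2.** "MTD is defined as the highest dose level in which 6 patients have been treated and one or fewer patient experiences DLT". The phase I table in 9.2 ends at level 1; Table 1 in section 4 goes on to +2 and +3.
- **Section 4.2.3.1.** DLT events are those "possibly related to study drug occurring during the first 4 weeks (1 cycle) of therapy". Section 9.3.2 monitors DLT continuously in phase II.

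**The concern.** A 3+3 design protects patients because a level that fails is not given again. Here that protection is written for cohorts entering the trial. The separate permission for an individual patient to go up has no matching condition. The drafters saw the issue for +2 and +3: 4.3 restarts the DLT window at the new dose and closes a level that does badly. Leaving out level 1 after a lower MTD, and leaving out phase I patients, looks like an oversight.

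What is at stake is exposure of patients in cytogenetic remission, or at least in chronic phase, to a dose of the combination that phase I has found too toxic or has not finished testing. Scheduled surveillance is lighter by then. Blood counts and chemistry every 1 to 2 weeks end at 8 weeks and then fall to once per cycle (5.2.2, 5.2.4), and the phase II toxicity evaluation is every 3 months (5.2.1.2).

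**Working it through.** **Plan's own figure.** The plan gives none for individual escalation. Its phase II power (9.4) reproduces: rejecting at 5 or more of 36 gives exact one-sided alpha 0.032 at 5% and power 0.873 at 20%, against the stated 87%. Nothing below touches it.

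**Step 1: which moves have an MTD check.**

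| Patient | Move | Explicit check |
|---|---|---|
| Phase II, dose is level 1 | 1 to +2, +2 to +3 | 33% first-cycle rule, 4.3 |
| Phase II, dose is level 0 because level 1 failed | 0 to 1 | none |
| Phase I | 0 to 1, level 1 under evaluation or failed | none |
| Phase I | 1 to +2 or beyond | none clearly; 4.3 is worded for phase II |

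The last row has a further ambiguity. "The data from the 6 patients treated at the recommended phase II dose level" are used in phase II, so it is unclear whether those six fall under the 4.3 rule. A move to a level not yet opened is largely barred by 4.2.1 and is not part of this point. The step from level 0 to level 1 is 3 × 50 = 150 to 3 × 75 = 225 mg/m² per cycle.

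**Step 2: how often gap (a), the second row, could arise.** Level 1 must show 2 or more DLTs in up to 6 patients, and level 0, filled to 6, at most 1. With independent patients, and level 1 filled to six as 9.2.2 requires:

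P = [1 − (1−p₁)⁶ − 6p₁(1−p₁)⁵] × [(1−p₀)⁶ + 6p₀(1−p₀)⁵]

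The DLT rates are assumptions; the documents give none.

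| p₀ / p₁ | Level 1 fails | Level 0 holds | Product |
|---|---|---|---|
| 5% / 10% | 0.114 | 0.967 | 0.111 |
| 10% / 20% | 0.345 | 0.886 | 0.305 |
| 15% / 30% | 0.580 | 0.776 | 0.450 |

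A 200,000-run simulation of the 3+3 gives 0.111, 0.305 and 0.449. This is the chance of the precondition, not of any patient being escalated. All 36 phase II patients would then start from level 0; how many would qualify under 4.5.5 cannot be derived from the documents.

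**Step 3: timing of gap (b), phase I.** Accrual is 1 to 2 per month (9.1) and observation is 28 days = 0.92 month. Assume even spacing and 0 of 3 DLTs at level 0.

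- 1 per month: level 0 entries at 0, 1, 2; level 1 opens at 2.92; entries 2.92, 3.92, 4.92; three observed at 5.84. Level 0 patients reach month 3 at 3, 4, 5: all 3 before 5.84.
- 2 per month: entries 0, 0.5, 1; level 1 opens at 1.92; three observed at 3.84. Month-3 points 3, 3.5, 4: 2 of 3 before 3.84.

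If the decision waits for the next PCR after the first three cycles (before cycle 6 to 9 on one reading of 5.2.5, that is 4.60 to 7.36 months after entry), the counts fall to between 2 and 0 of 3 at 1 per month and 0 of 3 at 2 per month. These patients have reached the time point; fewer will qualify.

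**Step 4: are later DLTs counted in 9.3.2?** That section takes its DLT definition from a section 4.3.3, which does not exist; 4.2.3 is presumably meant. Read with 4.2.3.1, the window is the first 4 weeks of therapy, so a DLT after a month-3 escalation falls outside it. But 9.3.2 also speaks of any DLT and of stopping at any time, and hematologic DLT in 4.2.3.4 needs 6 or 8 weeks. The text does not settle it.

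**The case against.** The strongest case against is that the protocol makes its intent plain. Section 9.2.1.4 stops dose escalation once a level exceeds the MTD, 4.2.2 names that level the maximally administered dose, and 4.3 shows what should follow. Escalation is optional, candidates have had no grade 3 or higher toxicity, and an investigator who knows that level 1 failed is unlikely to use it. Individual safeguards also apply. Under 4.5.4, AZA must be withheld for related, clinically significant grade 3–4 toxicity and may resume one level lower, and there are hematologic hold and reduction rules. Section 2.4 describes azacitidine alone at 75 mg/m² for 7 days as well tolerated in MDS. All of this stands and limits the weight of the point. It does not remove it: the stopping rules are written for cohorts, 4.3 affirmatively allows other Table 1 levels for lack of improvement, and the 4.5.4 rules act after harm.

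Three stronger readings are tempting, and the documents do not support them:

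- *A reader might infer that phase II escalation in general has no MTD check.* At the default dose, level 1, the levels above are +2 and +3, and 4.3 closes them. Applied after each of up to 6 escalated patients (an assumption), the 33% rule closes a level with probability 0.29, 0.54, 0.73 or 0.86 at true DLT rates of 10%, 20%, 30% or 40%. A 3+3 evaluation that accepts 0 of 3 rejects it with 0.09, 0.29, 0.51 or 0.69. The rule is stricter, though it acts only after exposure.
- *A reader might infer that DLTs after escalation never enter 9.3.2.* Step 4 shows only that this is unclear.
- *A reader might infer that phase I patients should wait until six patients at level 1 are evaluated.* Under 4.2.2 and 9.2.1.2, 0 of 3 at one level already suffices to treat new patients at the next; 9.2.2 defines the MTD, not when a level may be used. Such a wait would push level 0 patients past the six cycles in 4.5.7, close to removing the option.

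**Conclusion.** The point holds in limited form. Section 4.5.5, read with 4.3, has no explicit bar on moving an individual patient to a level that exceeded the MTD when (a) level 0 has become the phase II dose, or (b) the patient was enrolled in phase I. Phase I patients moved to +2 or +3 are also not clearly under the 33% stop. Gap (a) matters more. Its precondition has probability 0.11 to 0.45 over the assumed DLT rates, and the number of patients then exposed is unknown. Gap (b) concerns a few patients, and its timing depends on accrual and on when the molecular result is available. The MTD from the assigned cohorts is unaffected, because it rests on DLTs in the first course. This is a wording gap worth closing, not a fault in the design.

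**What to change.** Add to 4.5.5:

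> In either phase, no patient may be escalated to or above a level declared to exceed the MTD. The 33% first-cycle DLT rule in 4.3 applies to every patient escalated to level +2 or +3, including those enrolled in phase I.

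Limiting 4.5.5 to phase II would not do: it leaves gap (a) open and the status of the six carried-over patients unclear. The two sentences still allow a phase I patient to move to a level that is open but not fully evaluated. I would accept that, since new patients are treated there on the same evidence.

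The cost is two sentences in an amendment. If level 1 fails, optional escalation is lost, probably for a few patients. No patients or visits are added, and sample size and power stay as they are.

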5.2. Evaluation During Study

- 5.2.1. Physical exam and evaluation of toxicity (clinic visit or telephone interview):
 - 5.2.1.1. Phase I portion: every 2 weeks for the first month, then every month for the first 3 months, then every 3 months (± 1 month) until month 6, then every 6 to 12 months.
 - 5.2.1.2. Phase 2 portion: every 3 months (± 1 month) until month 6, then every 6 to 12 months.
- 5.2.2. CBC, platelet, differential every 1-2 weeks for 8 weeks, then at the start of every cycle. Differential not required if $WBC \leq 0.5 \times 10^9/L$.
- 5.2.3. Bone marrow aspirate with cytogenetics or FISH every 3-6 months in year 1, then as clinically indicated.
- 5.2.4. Total bilirubin, SGPT or SGOT, and creatinine every 1-2 weeks for 8 weeks, then before each cycle.
- 5.2.5. Quantitative PCR (peripheral blood and/or bone marrow) before each cycle for 3 cycles, then every 3-6 cycles until one year, then every 6-12 cycles.
- 5.2.6. Peripheral blood and bone marrow for correlative studies every 3-6 months in year 1, then every 6-12 months. Methylation studies will also be done on days 5, 10 and 28 (all ± 3 days) of the first cycle. Not all optional samples may be collected. (Optional – Appendix A, B & C).

6. Criteria for Response

- 6.1. A favorable response for the primary endpoint is defined as a greater than a one-log reduction of BCR-ABL transcript levels from the baseline level at the time vaccination was initiated, or a disappearance of BCR-ABL transcripts (i.e., complete molecular response).

7. Criteria for Removal from Study

- 7.1. The patient receives CML-directed therapy other than TKI and AZA.
- 7.2. The patient develops disease progression defined as confirmed loss of CCyR, confirmed loss of CHR or transformation to accelerated or blast phase.
- 7.3. The dose of TKI is increased or new therapies for their leukemia are added.
- 7.4. The patient has a continuous interruption of imatinib therapy for greater than 6 weeks.
- 7.5. The patient withdraws consent.
- 7.6. The treating physician considers it in the best interest of the patient.
- 7.7. Pregnancy or suspected pregnancy

8. Adverse Event Reporting

- 8.1. Adverse event is any untoward medical occurrence that may present during treatment with a pharmaceutical product but which does not necessarily have a causal relationship with this treatment.

Adverse drug reaction is a response to a drug which is noxious and unintended and which occurs at doses normally used in man for prophylaxis, diagnosis, or therapy of disease or for the modification of physiologic function.

Assessing causal connections between agents and disease is fundamental to the understanding of adverse drug reactions. In general, a drug may be considered a contributory cause of an adverse event if, had the drug not been administered, 1) the event would not have happened at all, 2) the event would have occurred later than it actually did, or 3) the event would have been less severe.

The Investigator or physician designee is responsible for verifying and providing source documentation for all adverse events and assigning the attribution for each event for all subjects enrolled on the trial.

- 8.2. Adverse Events (AEs) will be evaluated according to the latest CTC version and documented in medical record. Only unexpected AEs will be recorded in the Case Report Form (CRF). Expected events during leukemia therapy are:

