The cytotoxicity of azacitidine is proportional to dose and exposure time.^{40,41} Although the mechanisms of cytotoxicity are complex and multifaceted, there is general agreement that incorporation of azacitidine into DNA and ribonucleic acid (RNA), and inhibition of protein synthesis, are critically important.⁵⁰ Cytotoxicity is greatest in cells that are proliferating (S phase) and metabolically active.⁴⁰ Cytotoxic effects may also be mediated through induction of the DNA damage response pathways.⁴⁹ Nonproliferating cells are relatively insensitive to azacitidine.⁴⁰

Toxicology studies have been conducted in mice, rats, dogs, and Rhesus monkeys.⁵¹ Most of the studies were performed during the 1970s and early 1980s according to existing guidelines and standards in place during that period. The preclinical studies identified the bone marrow, liver, kidneys, and lymphoid tissues (spleen, lymph nodes, and thymus) as the main target organs of toxicity for azacitidine.⁵¹ In single-dose studies, the lethal dose of azacitidine after intravenous (IV) administration in mice, rats, and dogs was approximately 250 mg/m². Repeated daily dosing appears to increase the toxicity of azacitidine.⁵¹ The genotoxicity of azacitidine is consistent with that of other nucleoside analogs that interact with nucleic acids.⁵¹ Likewise, similar to other agents with cytostatic properties, azacitidine was embryotoxic and reduced the reproductive performance in mice and rats.⁵¹

Limited azacitidine pharmacokinetic data are currently available. Based on human plasma concentrations of total radioactivity (which represents parent drug plus circulating metabolites), azacitidine is rapidly absorbed when given subcutaneously (SC), with maximum plasma concentrations found 0.5 to 2 hours after dosing.⁵¹ Azacitidine and/or its by-products are then rapidly cleared by the kidneys. The half-lives and percent radioactivity recovered in urine are similar following IV and SC routes of administration. The effects of renal or hepatic impairment, gender, age, or race on the pharmacokinetics of azacitidine have not been studied.⁵¹ A single dose (75 mg/m²) SC versus IV crossover study in 6 MDS subjects⁵² revealed an approximate bioavailability of 89% for the SC dose (range 52% to 128%) with mean half-lives of 0.69 hour and 0.36 hour after SC and IV administration, respectively. These results demonstrated that azacitidine is rapidly and nearly completely absorbed after SC

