- 3.1.10. Serum creatinine < 1.8 mg/dL or creatinine clearance greater or equal than 40 cc/min as defined by the Cockcroft-Gault Equation*. Males(mL/min): $(140 - \text{age}) * \text{ABW}(\text{kg}) / 72 * (\text{serum creatinine}(\text{mg/dl}))$; Females (mL/min): $0.85 * (140 - \text{age}) * \text{ABW}(\text{kg}) / 72 * (\text{serum creatinine}(\text{mg/dl}))$
- 3.1.11. Women of childbearing potential should be advised to avoid becoming pregnant and practice effective methods of contraception. Men should be advised not to father a child while receiving treatment with azacitidine. Azacitidine is classified as Pregnancy Category D. Females of childbearing potential: Recommendation is for 2 effective contraceptive methods during the study. Adequate forms of contraception are double-barrier methods (condoms with spermicidal jelly or foam and diaphragm with spermicidal jelly or foam), oral, depo provera, or injectable contraceptives, intrauterine devices, and tubal ligation. Male patients with female partners who are of childbearing potential: Recommendation is for male and partner to use at least 2 effective contraceptive methods, as described above, during the study.
- 3.1.12. Women of childbearing potential should have a pregnancy test within 7 days before initiation of study drug.

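### Pregnancy is tested once, before the first azacitidine dose, and no test is scheduled before any later, continuation or resumed cycle

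*Combined protocol and SAP*

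**What the plan says.** Two places in the combined protocol and SAP call for a pregnancy test, and both mean the same one. Inclusion criterion 3.1.12 reads "Women of childbearing potential should have a pregnancy test within 7 days before initiation of study drug", and pretreatment item 5.1.4 reads "Pregnancy test (blood or urine) for female patients of childbearing potential within 7 days before initiation of study drug dosing".

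The on-study schedule (5.2.1 to 5.2.6) covers examination and toxicity review, blood counts, marrow, chemistry, PCR and correlative samples. It has no pregnancy test. The chemistry line, 5.2.4, is "Total bilirubin, SGPT or SGOT, and creatinine every 1-2 weeks for 8 weeks, then before each cycle".

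Dosing is repeated. Section 4.4 says "Treatment with AZA (in both phase I and phase II) may be repeated every 28 days" and 4.5.7 says "Patients may receive therapy for six cycles". Section 4.5.7 also permits continuation after cycle 6, and 4.5.7.1 permits a restart after a hold. None of these makes a pregnancy test a condition.

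On fetal risk, 3.1.11 states "Azacitidine is classified as Pregnancy Category D", and the background in 2.4 reports that "azacitidine was embryotoxic and reduced the reproductive performance in mice and rats". Contraception is handled as advice: "Recommendation is for 2 effective contraceptive methods during the study". Section 7.7 removes a patient for actual or suspected pregnancy, and 8.6 requires azacitidine to be stopped immediately and the pregnancy to be reported within 24 hours.

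**The concern.** A negative result before cycle 1 says nothing about conception afterwards, yet a drug the protocol treats as a fetal hazard is given again every 28 days. The provisions in 7.7 and 8.6 govern the response to a pregnancy. Nothing scheduled would find one. Detection therefore depends on the patient noticing and reporting, on a clinician's suspicion, or on an unscheduled test.

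At stake is avoidable, possibly irreversible fetal exposure during later courses. The gap is widest after a hold under 4.5.7.1: the only scheduled test may by then be many months old, and the monitoring named there is PCR.

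**Working it through.** The plan gives no figure to reproduce here. The check sets the testing schedule against the dosing schedule and counts.

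**Inputs from the protocol**
- One pregnancy test, within 7 days before first dosing (3.1.12, 5.1.4)
- Cycle length 28 days (4.4)
- Six planned cycles (4.5.7)
- Phase II examination and toxicity review every 3 months, ± 1 month, to month 6, then every 6 to 12 months, in clinic or by telephone (5.2.1)
- 48 patients in total (9.1)

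**Tested and untested cycle starts.** Without delays, cycle k starts on day 1 + 28(k − 1):

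| Cycle | 1 | 2 | 3 | 4 | 5 | 6 |
|---|---|---|---|---|---|---|
| Start day | 1 | 29 | 57 | 85 | 113 | 141 |
| Scheduled pregnancy test | yes | no | no | no | no | no |

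So 6 − 1 = 5 planned starts have no test, and neither does any continuation or resumed cycle.

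**Courses before the first phase II review.** At 30.4 days per month, months 2, 3 and 4 end at about days 61, 91 and 122 of treatment, that is, near study days 62, 92 and 123. Starts after day 1 by then:
- month 2: days 29 and 57, so 2 courses
- month 3: also day 85, so 3 courses
- month 4: also day 113, so 4 courses

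Between 2 and 4 further courses can therefore begin before the first scheduled examination or toxicity review. Phase I reviews are closer together (every 2 weeks in month 1, then monthly to month 3), so this count applies to phase II only.

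**Courses between later reviews.** After month 6 the interval is 6 to 12 months: 6 × 30.4 / 28 = 6.5 and 12 × 30.4 / 28 = 13.0. Roughly 6 to 13 continuation courses fit between two reviews.

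**Number of added tests.** The documents do not say how many patients are women of childbearing potential. The share is assumed:

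| Assumed share of 48 | Women | Added tests, cycles 2-6 (× 5) |
|---|---|---|
| 10% | 4.8, taken as 5 | 25 |
| 25% | 12 | 60 |
| 50% | 24 | 120 |

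These are counts of tests, not of pregnancies.

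**The case against.** The strongest reply is that this is a preference. Nothing in the documents promises testing at every cycle, no part of the plan fails without it, and the benefit cannot be quantified. Safeguards exist: pregnant patients are excluded (3.2.2), women are advised on effective contraception with acceptable methods listed (3.1.11), suspicion alone is enough for removal (7.7), and continuation needs the investigator's judgement of benefit (4.5.7). All of that is true. It lowers the risk, but none of it detects a pregnancy that nobody suspects.

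A second reply is that patients are seen often. Azacitidine is given by injection or infusion, with blood counts and chemistry every 1-2 weeks and then each cycle. The count of 2 to 4 courses is indeed courses before one listed review, not courses without contact. But the listed laboratory tests do not show pregnancy; the contacts mainly show how easily a test could be added.

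Three practical points about the remedy have some force:
- In the first 8 weeks, 5.2.4 does not guarantee a draw within 7 days of a cycle. The pre-cycle PCR samples in 5.2.5 or a urine test at the dosing visit fill that gap.
- Waiting for a negative result adds a hold point, and a false positive could trigger 7.7. A prompt repeat test settles the latter.
- A very early pregnancy can be missed, and conception after the test is not prevented. Repeat testing limits repeated exposure; it does not remove all exposure.

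The consent pages and Appendices A-C are not available, but the appendices are cited only for optional correlative samples, and the schedule in section 5 is shown in full.

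**Conclusion.** The concern holds. One of six planned cycle starts has a scheduled pregnancy test; five do not, nor does any continuation or resumed cycle. In phase II, 2 to 4 further courses can start before the first scheduled examination or toxicity review, and that review includes no test either.

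These counts assume undelayed 28-day cycles and a patient who completes all six. The number of exposures that might result cannot be estimated from the documents and may be small. This is a safety-monitoring gap that should be closed because the potential harm is serious and the remedy is slight. It does not bear on the primary endpoint, the sample size or the power.

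**What to change.** Add one line to 5.2: for women of childbearing potential, repeat the blood or urine test of 5.1.4 within 7 days before each azacitidine cycle, including continuation cycles and any restart after a hold, and give azacitidine only after a negative result. State that a positive result is confirmed by a prompt repeat before removal under 7.7, with dosing held meanwhile.

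The cost is five tests per woman over six cycles, at draws or dosing visits that already take place, plus one per continuation cycle or restart. Under the 10-25% assumption that is 25 to 60 tests for the trial. That a test is inexpensive is a judgement; the documents give no price.

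A further test about 28 days after the last dose is optional. It would support the reporting duty in 8.6 but cannot prevent another course. It brings the total to six tests per woman: 5 × 6 = 30 to 12 × 6 = 72. Pregnancies in partners of male patients would remain covered by 8.6 reporting alone.
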